ABR	ABR form, General Assessment and Registration form, is the application form that is required for submission to the accredited Ethics Committee (In Dutch, ABR = Algemene Beoordeling en Registratie)
ACEi	Angiotensin Converting Enzyme Inhibitor
AE	Adverse Event
AR	Adverse Reaction
ARB	Angiotensin Receptor Blocker
CA	Competent Authority
CCMO	Central Committee on Research Involving Human Subjects; in Dutch: Centrale Commissie Mensgebonden Onderzoek
CV	Curriculum Vitae
DSMB	Data Safety Monitoring Board
EU	European Union
EudraCT	European drug regulatory affairs Clinical Trials
GCP	Good Clinical Practice
IB	Investigator's Brochure
IC	Informed Consent
IMP	Investigational Medicinal Product
IMPD	Investigational Medicinal Product Dossier
METC	Medical research ethics committee (MREC); in Dutch: medisch ethische toetsing commissie (METC)
(S)AE	(Serious) Adverse Event
SGLT2	Sodium Glucose Transport Inhibitor 2
SPC	Summary of Product Characteristics (in Dutch: officiële productinfomatie IB1-tekst)
Sponsor	The sponsor is the party that commissions the organisation or performance of the research, for example a pharmaceutical company, academic hospital, scientific organisation or investigator. A party that provides funding for a study but does not commission it is not regarded as the sponsor, but referred to as a subsidising party.
SUSAR	Suspected Unexpected Serious Adverse Reaction
Wbp	Personal Data Protection Act (in Dutch: Wet Bescherming Persoonsgevens)

WMO Medical Research Involving Human Subjects Act (in Dutch: Wet Medisch-wetenschappelijk Onderzoek met Mensen)

SUMMARY

Rationale:

Despite optimal treatment with renin-angiotensin-aldosterone-system (RAAS) inhibitors, many patients with non-diabetic kidney disease show progressive kidney function loss, which is associated with high residual albuminuria. Novel treatment strategies are therefore required to further decrease albuminuria and to slow kidney function decline.

Dapagliflozin is a sodium-glucose transport (SGLT2) inhibitor and inhibits the reabsorption of glucose and sodium in the proximal tubule. The increased natriuresis following dapagliflozin administration normalizes tubuloglomerular feedback resulting in a reduction in intraglomerular hypertension, which is in turn manifested by acute reductions in glomerular filtration rate and albuminuria. Since many etiologies of non-diabetic nephropathy are characterized by intraglomerular hypertension, we hypothesize that dapagliflozin acutely decreases GFR and albuminuria in patients without diabetes at risk of progressive kidney function loss via a glucose independent hemodynamic mechanism.

Objective:

Primary:

- To assess the change baseline in 24-hr proteinuria with dapagliflozin for six weeks relative to placebo treatment in patients with non-diabetic kidney disease and proteinuria > 500 mg/day on stable ACEi or ARB treatment.

Secondary:

- To assess the effect of dapagliflozin 10 mg/d compared to placebo on Glomerular Filtration Rate (GFR) using iohexol clearance.
- To assess the effect of dapagliflozin 10 mg/d compared to placebo on systolic/diastolic blood pressure
- To assess the effect of dapagliflozin 10 mg/d compared to placebo on body weight
- To assess the effect of dapagliflozin 10 mg/d on selected neurohormones/biomarkers:
 - Hormones of the RAAS (plasma and urine)
 - Natriuretic peptides
 - Urinary adenosine
 - Co-peptin

- Immunoglobulin G (plasma and urine)
- To characterize the safety of dapagliflozin vs. placebo by determining the number of hypoglycemic episodes between groups, and serious adverse events.

Study design:

Randomized placebo controlled double blind cross-over trial

Eligible participants will be randomly assigned to one of the two treatment orders: placebo-dapagliflozin or dapagliflozin-placebo. Each treatment period lasts 6 weeks followed by a 6 week wash-out period to avoid cross-over effects. Patients will have their study visit in the morning in fasted condition.

Study population: Male and female subjects with Chronic Kidney Disease aged between 18 and 75 years, proteinuria levels between 500 and 3500 mg/24-hour, and an eGFR \geq 25 ml/min/1.73m² will be enrolled. Patients with type 1 or type 2 diabetes, polycystic kidney disease, glomerulonephritis with flares (lupus or anti-neutrophil cytoplasmic antibodies (ANCA) associated vasculitis) or ongoing active renal inflammation will be excluded. Patients have to be treated with a stable dose of an ACEi or ARB for at least 4 weeks prior to enrolment.

Intervention: Dapagliflozin 10 mg/day or matched placebo

Main study parameters/endpoints: Change in 24-hr proteinuria

Nature and extent of the burden and risks associated with participation, benefit and group relatedness: Patients visit the outpatient clinic on a more regular base than standard patient care - i.e. at study inclusion and at start and end of each treatment period (9 hospital visits in a total study duration of 25 or up to 41 weeks) - for clinical assessment. A fasting blood sample is collected with venipuncture. Non-radioactive iohexol GFR measurements are performed at start and end of each treatment period as well as at the end of the wash-out period. 24hr urine will be collected one day prior to the hospital visit, except for the screening visit when patients collect 24hr urine after informed consent is obtained. No other invasive measurements will be executed. Patients receive restitution of all travel costs. Patients receive no priority in treatment of other diseases in the clinic during this study. There are no direct benefits for the patients to be included and participation is on a voluntary basis.

1. INTRODUCTION AND RATIONALE

Inhibition of sodium–glucose cotransporter 2 (SGLT2i) reduces plasma glucose and HbA1c in patients with type 2 diabetes by increasing urinary glucose excretion. Beneficial effects of SGLT2i beyond glycemic control in patients with type 2 diabetes have been suggested by the EMPA-REG OUTCOME trial, in which empagliflozin treatment added to standard care significantly reduced the composite primary endpoint (i.e. death from cardiovascular causes, nonfatal myocardial infarction, or nonfatal stroke), compared to participants allocated to the placebo group ¹. In this study, dramatic cardiovascular protective effects were reported, even though HbA1c was only reduced by 0.36% at the end of the study. The preliminary renal outcome data were recently reported showing that individuals treated with empagliflozin had a 39% reduced risk of new onset of nephropathy; and a 46% reduced risk of the composite renal endpoint consisting of doubling of serum creatinine, end stage kidney disease (ESKD) or death due to renal disease ². In light of modest glucose-lowering effects in EMPA-REG Outcome, renal and cardiovascular benefits have been attributed to natriuretic properties of the class, leading to hemodynamic effects in both the renal and systemic vascular circulations.

In the renal microcirculation, SGLT2i “normalizes” tubuloglomerular feedback mechanisms seen in the hyperfiltration stage of diabetic nephropathy ³. Furthermore, effects of SGLT2i at the afferent arteriole likely account for the acute “dip” in eGFR observed in patients with and without impaired renal function, which likely reflects a reduction in intraglomerular hypertension at the single nephron level across the spectrum of renal function. It is believed that natriuresis leading to increased tubuloglomerular feedback at least partially mediates the beneficial effects of SGLT2i via this glucose-independent hemodynamic mechanism. However, it is unclear if the renal protection of SGLT2i can be similarly applied to other proteinuric kidney diseases that are unrelated to diabetic nephropathy.

One of the general physiological principles that applies to progression of both diabetic and non-diabetic chronic kidney disease (CKD) is the concept of elevated intraglomerular pressure as a risk factor for CKD progression. More specifically, in the setting of CKD, remnant nephrons can hyperfunction – or hyperfilter - to compensate for the loss of mass due to injury from the primary disease. What started as a compensatory mechanism to maintain GFR through elevated single nephron filtration becomes a maladaptive response leading to glomerular hypertrophy and hyperfiltration over time. Intraglomerular hypertension is thought to ultimately contribute to progressive loss of renal function in diverse glomerular nephropathies, including focal segmental glomerular sclerosis, IgA nephropathy and membranous glomerulonephritis ⁴.

To reduce intraglomerular hypertension, current guidelines recommend the use of RAAS blockers as the gold standard therapy for individuals with non-diabetic nephropathy and proteinuria⁵. However, despite the use of these agents, renal function continues to decline. Therefore, there is a need to widen the therapeutic armamentarium for individuals with non-diabetic nephropathy. SGLT2i lowers the threshold of proximal glucose reabsorption resulting in glycosuria, and increases distal tubular sodium delivery to macula densa cells. Macula densa cells are specialized epithelial cells located at the distal convoluted tubule that sense sodium delivery and mediate afferent arteriolar vasoconstriction in response to an increase in tubular sodium. SGLT2 inhibition increases the delivery of glucose and sodium in the distal tubule and to the juxtaglomerular apparatus, which is sensed as an increase in glomerular perfusion. This leads to a tubuloglomerular feedback signal causing afferent arteriolar vasoconstriction, and acute fall in intraglomerular pressure. These effects are clinically manifested as acute reductions in GFR and hence albuminuria, followed by renal function preservation in the longer term – as recently reported in EMPA-REG Outcome. Furthermore, natriuresis diminishes extracellular plasma volume and blood pressure. Thus, SGLT2i specifically alters renal hemodynamic function by reducing intraglomerular pressure, which could be expected to translate into improved long-term kidney outcomes - including individuals without diabetes.

SGLT2i are oral anti-hyperglycemic agents that decrease HbA1c through insulin-independent effects via glycosuria. They therefore have negligible hypoglycemic risk as compared to other classes of anti-hyperglycemic agents, since the degree of glucose lowering depends on the filtered load of glucose which, in non-diabetic patients, is very low^{6, 7}. The low risk of hypoglycemia offers the opportunity to test these drug classes in non-diabetic proteinuric renal disease.

In conclusion, SGLT2i has a plausible therapeutic potential in individuals with non-diabetic nephropathy at risk of renal progression, and are likely to be well tolerated. Exploring the beneficial effects of these agents in non-diabetic proteinuric kidney disease may pave the way for a new indication for this class of drugs. In addition, trials in non-diabetic kidney disease may help to further characterize the non-glucose dependent effects, which may help to differentiate SGLT2i from other glucose lowering agents.

2. OBJECTIVES

Primary Objective:

- To assess the change from baseline in 24-hr proteinuria with dapagliflozin for six weeks relative to placebo treatment in patients with non-diabetic kidney disease and proteinuria > 500 mg/day on stable ACEi or ARB treatment.

Secondary Objectives

- To assess the effect of dapagliflozin 10 mg/d compared to placebo on Glomerular Filtration Rate (GFR) using iothexol clearance
- To assess the effect of dapagliflozin 10 mg/d compared to placebo on systolic/diastolic blood pressure
- To assess the effect of dapagliflozin 10 mg/d compared to placebo on body weight
- To assess the effect of dapagliflozin 10 mg/d compared to placebo on selected neurohormones/biomarkers:
 - Hormones of the RAAS (plasma and urine)
 - Natriuretic peptides
 - Urinary adenosine
 - Co-peptin
 - Immunoglobulin G (plasma and urine)
- To characterize the safety of dapagliflozin vs. placebo by determining the number of hypoglycemia episodes between groups and serious adverse events.

3. STUDY DESIGN

A double blind randomized placebo controlled cross-over study will be conducted in subjects with Chronic Kidney Disease aged between 18 and 75 years, proteinuria levels between 500 and 3500 mg/24-hour, and an eGFR ≥ 25 ml/min/1.73m² will be enrolled. Patients with type 1 or type 2 diabetes, polycystic kidney disease, glomerulonephritis with flares (lupus or anti-neutrophil cytoplasmic antibodies (ANCA) associated vasculitis) or ongoing active renal inflammation will be excluded. Since each subject is his/her own control, this design requires fewer patients as compared with a parallel study design. A wash-out period after each treatment period has been included in the design to avoid cross-over effects.

The study will consist of a screening visit, a 4-week (up to a maximum of 16-weeks) run-in phase for those subjects not on stable ACEi/ARB treatment, 2 consecutive 6-week double blind treatment periods separated by 6-week wash-out period. Subjects will be randomly assigned to one of the treatment orders as depicted in figure 1.

Figure 1: Study design

Screening	Run-in 4 weeks	Placebo 6 weeks	Wash-out 6 weeks	Dapa 10 mg 6 weeks	Wash-out 6 weeks
Screening	Run-in 4 weeks	Dapa 10 mg 6 weeks	Wash-out 6 weeks	Placebo 6 weeks	Wash-out 6 weeks

The target population will be invited for screening. Subjects who meet all entry criteria and who are already on a stable dose (no changes in dose or type of drug) of ACEis or ARBs for at least 4 weeks proceed directly to randomization. Subjects who had their ACEi or ARB medication changed during the preceding 4 weeks of the screening visit proceed to a run-in phase during which the type and dose of these drugs are stabilized. Subjects will be randomly assigned to one of the two treatment orders as depicted in figure 1. Each treatment period lasts 6 weeks followed by a 6 week wash-out period to avoid cross-over effects. Subjects will have their study visit in the morning in fasted condition.

Subjects will be instructed to take the study medication once daily, in the morning, except on study days; on those days, the study drug will be taken after or during the patient visit.

Measurements:

- During the double blind treatment period, and wash-out period patients will collect a 24-hour urine collection at each visit for measurement of 24-hour protein, albumin, sodium,

potassium, creatinine, and urea excretion. Twenty-four hour urine collections will be performed at:

- o Screening visit
- o Run-in, day 1, week 3, and week 6 (last day on treatment) of each treatment period, and six weeks after the second treatment period (after the last wash-out period).
- Office systolic and diastolic blood pressure measurements will be performed at day 1, week 3 and 6 (last day on treatment) of each treatment period, and six weeks after the second treatment period.
- Vital signs (heart rate, blood pressure) and body weight, height
- Blood will be sampled for measurement of laboratory assessment outlined in the Table 1 and analysis will be performed by the local laboratory.
- Additional blood will be sampled at Day 1 and week 6 of each treatment period, and six weeks after the second treatment period for shipment to the UMCG for biomarker measurement including RAAS biomarkers, natriuretic peptides, co-peptin, immunoglobulin G, and urinary adenosine.
- Blood and urine samples will be stored for future exploratory biomarker analyses to study the effect of dapagliflozin in this study population
- At the screening visit Demography and significant medical history as defined below will be assessed and recorded on the Medical History/Kidney Diagnosis section of the eCRF.
 - Kidney diagnosis
 - Condition related to kidney disease (i.e. recurrent electrolyte disturbances, hypovolemia, prior events such as Acute Kidney Injury)
 - Cardiovascular diseases
 - Recurrent/severe urinary tract infections, genital infections, urosepsis
 - Recent hospital admission, and reason for admission (within the last year)
 - Reactions to radio-contrast media

- **Time and Events Table**

Parameter	Screening ^a	Run-in	Treatment Period 1				W/O	Treatment Period 2				W/O
Visits	V0	V1	V2	V3	V4	V5		V6	V7	V8	V9	V10
Week			0	1	3	6		12	13	15	18	24
Informed Consent ^a	x											
Randomization			x									
Significant Medical History & Kidney disease diagnosis	x											
Serum or Urine Pregnancy test			x ^c					x ^{c, g}				
24-hour urine ^b	x ^d	x	x		x	x		x		x	x	x
GFR-iohexol			x			x		x			x	x
Plasma PK sample						x					x	
Vital signs	x	x	x		x	x		x		x	x	
Blood sampling ^e	x	x	x		x	x		x		x	x	x
Additional blood sampling			x			x		x			x	x
'Biomarker samples' ^f												
Physical exam	x		x		x	x		x		x	x	x
Telephone visit				x					x			
Dispense Medication			x					x				
Drug accountability						x					x	
Adverse events	x	x	x	x	x	x		x	x	x	x	x
Review medications	x	x	x		x	x		x		x	x	
DNA collection			x									

a Informed consent is obtained before any study specific procedure is done.

b Total 24-hr urinary dapagliflozin excretion will also be measured at the end of each treatment period

c WOCBP must have a negative serum or urine pregnancy test result (minimum sensitivity 25 IU/L or equivalent units of HCG) within 0 to 72 hours before the first dose of study drug.

d Subject will be asked to collect 24 hour urine after informed consent is obtained. The subject will be requested to return the urine sample to the site on the following day.

e Specify details about specimen collection will be provided in the laboratory manual. Table 1-2 will list the laboratory assessment to be performed.

f Specify details about specimen collection, storage and processing will be provided in the laboratory manual.

g Visit 6 Serum or Urine Pregnancy Test is required for Canada sites per local regulatory requirement

Study Periods and Procedures:

Screening

Chronic Kidney Disease aged between 18 and 75 years, proteinuria levels between 500 and 3500 mg/24-hour, and an eGFR ≥ 25 ml/min/1.73m² who are on an ACEi or ARB, or can start with an ACEi or ARB, will be eligible for protocol-specific assessment during the screening period. Signature of the protocol-specific informed consent form constitutes the first procedure of the screening period, followed by the assignment of a unique subject number. Protocol-specific assessments and procedures may then be performed, as part of the screening visit, to evaluate the subject's eligibility. During the screening period, subjects will maintain their stable doses of commercially available ACEis or ARBs, and diuretic medication.

When all inclusion and exclusion criteria have been evaluated and the requirements for entry into the study have been met, the entry into run-in period or double blind treatment period will be scheduled. If the patient does not qualify based on the laboratory data, the patient is allowed to be re-screened within 3 weeks of the original screening date. The laboratory data based on which the patient failed should be repeated.

Run-in Period:

Potentially eligible subjects who complete the screening visit will enter the run-in period if they are not using an ACEi or ARB, or if they are not using a maximum tolerated dose of an ACEi or ARB. During the run-in period, ACEi or ARB will be started or uptitrated towards the maximum tolerated antihypertensive dose. If a patient does not tolerate the maximum dose of an ACEi or ARB, this should be documented in the eCRF and the patient can proceed to the double blind treatment period if all other entry criteria are met.

Visit 1

Subjects who entered the run-in period will return for the run-in visit 4 weeks after starting an ACEi/ARB or after ACEi/ARB dose adjustments. The subject has to be on a stable dose of an ACEi or ARB for at least 4 weeks before randomisation. More visits may be required to make sure that the subject still meet all entry criteria at the end of the run-in period. The run-in period may take up to a maximum of 16 weeks. If the eGFR remains ≥ 25 ml/min/1.73m² and the proteinuria level remains between 500 mg/24hr and ≤ 3500 mg/24hr at the end of the run-in period, the patient qualifies to proceed to the double blind treatment period.

Double-Blind Treatment Period:

Eligible subjects will enter in the randomized, double-blind, treatment period if their ACEi/ARB and diuretic medication is stable for at least 4 weeks and all entry criteria are met. The

randomization codes generated by University Medical Center Groningen will be programmed into the IBM Clinical Development Merge to randomly assign subjects to a treatment arm. The investigational drug will be dispensed by the principal investigator or delegated based on the randomization number.

Subjects will continue to maintain their stable doses of commercially available ACEI or ARB, and diuretics if applicable, throughout the double blind phase. Patients will be counseled to maintain a stable habitual dietary salt intake

Visit 2

The randomization visit procedures should be completed on a single day. The randomization visit procedures will include GFR measurement by plasma clearance of nonradioactive iohexol after a single intravenous dose. The GFR measurement will last approximately 4 hours for patients. The first dose of blinded study medication should only be administered on Day 1 AFTER ALL randomization visit procedures have been completed. Patient will be treated in random order with dapagliflozin 10 mg QD or matching placebo QD.

Visit 3, 4, and 5

Subjects will be followed for a total of 6 weeks on double-blind study medication in each active treatment period. A telephone visit will be scheduled after 1 week to assess tolerability. If the patient does not tolerate medication a visit to the out-patient clinic will be scheduled. The next scheduled visit (visit 4) occurs 3 weeks after randomization. A visit window of +/- 3 days is allowed for each out-patient clinic visit. Patients are asked to collect a 24-hr urine and blood will be sampled for clinical chemistry measurement. The last scheduled visit in the first treatment period is scheduled after 6 weeks. The last visit of the treatment period will include GFR measurement by plasma clearance of nonradioactive iohexol after a single venous dose, collection of a 24-hr urine sample and clinical chemistry measurements. At the end of the treatment period, the patient will take study medication *BEFORE* the GFR measurement procedure. In addition to using blood samples for GFR measurements, the samples will also be used to measure plasma concentration dapagliflozin and its metabolite dapagliflozin-3-O-glucuronide.

Visit 6,7,8, and 9

Following the last visit of the first treatment period subjects proceed to a 6 weeks wash-out period. After 6 weeks the second double blind treatment period will start. All visits and procedures in the second treatment period are similar to the first treatment period.

Visit 10

Six weeks after the second treatment period another visit will be scheduled. Procedures during this visit include GFR measurement with non-radioactive iohexol, 24-hr urine collection, blood pressure recording and blood sampling for clinical chemistry assessment.

Subjects who discontinue prematurely from the treatment period prior to visit 4, will have an abbreviated Week 12/ET visit, which will exclude measurements of GFR.

Clinical Lab Assessments

All protocol required local laboratory assessments, as defined in Table 1-2, must be conducted in accordance with the Laboratory Manual, and Time and Event Table.

Table 1

Plasma Laboratory Assessments		Parameters	
Hematology		Hemoglobin	Hematocrit
Clinical Chemistry	Urea	Bilirubin	
	Creatinine	Phosphate	
	AST	Calcium	
	ALT	Glucose	
	Total Protein		
Lipid Parameters	LDL	HDL	
Electrolytes	Sodium	Potassium	
	Chloride	Bicarbonate	
Other Laboratory Test	NT-proBNP ¹	HbA1C	
	Urine/Serum		
	Pregnancy Test ²		

¹ Sites that are unable to perform NTproBNP will arrange for samples to be sent to UMCG for central analysis.

² Pregnancy test: negative serum or urine pregnancy test result (minimum sensitivity 25 IU/L or equivalent units of HCG) within 0 to 72 hours before the first dose of study drug.

Table 2

24-Hour Urine Laboratory Assessments		Parameters	
Clinical Chemistry	Sodium	Creatinine	
	Potassium	Albumin	
	Urea	Protein	

Biomarker analysis

Serum, plasma and urine will be collected and stored for potential future analysis for exploratory biomarkers to assess correlations with disease activity and effects of study drug. These samples will be shipped and stored to a central storage facility in Groningen. The results of this biomarker research will be reported either in the main publication, or separately in a scientific report or publication. The results of this biomarker research may be pooled with biomarker data from other dapagliflozin studies to generate hypotheses to be tested in future research. Potential biomarkers to be measured include plasma albumin, RAAS biomarkers, natriuretic peptides, co-peptin, immunoglobulin G, urinary adenosine, and urinary vesicles.

DNA

Patients are asked to donate DNA as well. Participation in the pharmacogenetics study is optional and DNA will only be collected if patients consented for participation in this part of the study.

STUDY POPULATION

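### Women of child-bearing potential whom the run-in newly starts on an ACEi or ARB have no mandated pregnancy test before that start; the first scheduled test comes at least 25 days later

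*Protocol*

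**What the plan says.** **Who can enter untreated.** Under Screening, protocol section 3 opens eligibility assessment to patients "who are on an ACEi or ARB, or can start with an ACEi or ARB". The Run-in Period text sends those not using either drug into the run-in and then directs treatment: "During the run-in period, ACEi or ARB will be started or uptitrated towards the maximum tolerated antihypertensive dose". For them the drug start is a step of the protocol.

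**How long before randomisation.** The Visit 1 text and inclusion criterion 3.2 both require four weeks or more of stable ACEi or ARB dosing before randomisation. The run-in may last up to 16 weeks. The first dose of blinded study drug is given on Day 1, after the randomisation visit (V2) procedures.

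**When pregnancy is tested.** The row "Serum or Urine Pregnancy test" in the Time and Events Table is marked at V2 and V6 and is blank at V0 and V1. Footnote g makes the V6 test a requirement for Canadian sites. Footnote c, Table 1 footnote 2 and inclusion criterion 3.2 give the same timing: "within 0 to 72 hours before the first dose of study drug". The SAP (section 4) repeats that criterion and adds no earlier test.

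**What else applies before the run-in.** Section 3.3 excludes pregnancy, and section 3.2 requires contraception throughout the study. The Screening text schedules run-in entry only "When all inclusion and exclusion criteria have been evaluated and the requirements for entry into the study have been met".

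**The concern.** The protocol excludes pregnant women, and before study drug it does not rely on contraception alone: it also asks for a negative test of stated minimum sensitivity. The ACEi or ARB start in the run-in is another drug start that the protocol directs, it comes earlier, and it has no such mandated step.

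If the schedule is followed exactly, a woman with an unrecognised pregnancy at V0 could be started on a background drug and take it for weeks before any scheduled test applies the trial's own exclusion. She would also complete a run-in of 4 to 16 weeks for a trial she cannot enter.

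The matter is one of patient safety and schedule consistency. The estimand, power and type I error are not affected.

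**Working it through.** The plan states no figure for this gap, so there is none to reproduce. The check is date arithmetic on the protocol's own limits.

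**Inputs**
- Minimum stable dosing before randomisation: 4 weeks = 4 × 7 = 28 days (section 3, Visit 1; section 3.2).
- Maximum run-in: 16 weeks = 16 × 7 = 112 days (section 3, Visit 1).
- Longest lead of the test before first study drug: 72 hours = 3 days (footnote c; Table 1 footnote 2; section 3.2).
- First study drug: Day 1, at V2 (section 3, Visit 2).

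**Formula.** Days from ACEi or ARB start to first scheduled test = days from start to V2 − lead of the test before first dose.

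| Case | Test 72 hours before first dose | Test on the day of first dose |
|---|---|---|
| Start at day 0, V2 at the 4-week minimum | 28 − 3 = 25 days | 28 − 0 = 28 days |
| Start at day 0, full 16-week run-in, V2 directly after | 112 − 3 = 109 days | 112 − 0 = 112 days |

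**Is 25 days a true floor?** The visit window of ± 3 days would lower it to 25 − 3 = 22 days only if it overrode the four-week minimum. That minimum is an inclusion criterion, so 25 days stands. Any dose increase after the start restarts the stable-dose period and lengthens the gap.

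**Is 112 days a maximum?** Not strictly. The protocol sets no limit between the end of the run-in and V2.

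**Could the mandated test be done before the run-in instead?** No. It must fall within 3 days before first study drug, and a new starter is at least 28 days away from that dose at run-in entry. The eligibility review before the run-in can cover the pregnancy exclusion, but it cannot satisfy the negative-test criterion for her.

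**Does Table 1 already schedule a test at V0?** Blood sampling is marked at V0, footnote e points to Tables 1 and 2, and Table 1 lists a pregnancy test. However, Table 1 footnote 2 fixes that test to the days before study drug, and the dedicated row is blank at V0 and V1. So no earlier test is scheduled.

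**After the fix.** With a negative result required from V0 before the start, no interval remains between the start and the first scheduled test.

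**The case against.** Four arguments carry weight on the other side.

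- **The harm is not in the documents.** They do not describe any risk of an ACEi or ARB in pregnancy. This stands, and the point uses no such risk. It rests only on the protocol applying its pregnancy exclusion by test before one protocol-directed drug start and not before another.
- **The two drugs differ.** Dapagliflozin is the investigational product, given for a mechanistic purpose. RAAS blockade is described in section 1 as guideline-recommended therapy for these patients. A stricter rule for the investigational product is defensible. This lowers the priority, but it does not show that the earlier test was considered and judged unnecessary.
- **Safeguards exist.** The pregnancy exclusion is evaluated before run-in entry, contraception is required, a test precedes study drug, and a site may test at screening if it wishes. All of this stands. A reader might infer that only history and contraception protect these women at the start. The documents do not support that: no text limits how the exclusion is checked. The accurate statement is that a test is not mandated.
- **The group may be very small.** The plan is to enrol 53 subjects, and those already on a stable dose "of ACEis or ARBs for at least 4 weeks proceed directly to randomization". The number of women of child-bearing potential not taking either drug at screening is not given and could be zero.

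A reader might also extend the point to dose increases in women already taking an ACEi or ARB, since the Run-in Period text also brings patients in "if they are not using a maximum tolerated dose of an ACEi or ARB". The documents do not settle this. The general design text sends stable-dose patients straight to randomisation, and SAP section 3.1 describes the run-in only for those not on stable treatment. In any case, a test at that moment would not precede first exposure.

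**Conclusion.** The point holds for one group: women of child-bearing potential who are not using an ACEi or ARB at screening and whom the protocol starts on one in the run-in. For them no pregnancy test is mandated before the start. The first scheduled test comes at least 25 days after it, and about 109 to 112 days after it in the boundary case. The boundary figures assume that the drug is started at the beginning of a full 16-week run-in and that V2 follows directly.

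This does not show that pregnant women can be randomised, because the V2 test precedes study drug. Nor does it show that the pregnancy exclusion is ignored before the run-in. It is a cheap patient-safety improvement of low priority. The number of women affected cannot be stated from the documents, and the analysis is untouched.

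**What to change.** - Mark the existing pregnancy-test row at V0 for women of child-bearing potential who will newly start an ACEi or ARB in the run-in.
- Add one sentence to footnote c: for these women, a negative result is required before the ACEi or ARB is started.
- Keep the V2 test, because a V0 test cannot detect conception during the run-in.
- Leave dose increases in women already on an ACEi or ARB outside this change.

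**Cost.** One extra urine or serum test per affected woman, with no extra visit: blood sampling and a 24-hour urine collection are already marked at V0. Run-in entry need not be delayed, since ALT and AST from the screening visit must already be known, and the Screening text already deals with patients who fail on laboratory results ("If the patient does not qualify based on the laboratory data, the patient is allowed to be re-screened"). The document change is one table mark and one sentence at the next amendment. Sample size and analysis stay as they are.
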